### 7.9.1 When and How to Withdraw Subjects

Subjects may be withdrawn at the medical discretion of the physician, or they may voluntarily withdraw their consent at any time without impact to their medical treatment.

	No.: CP 65007	REV. C
	TITLE: Disrupt PAD BTK II Study	
	CLASS: CLINICAL PROTOCOL	PAGE 37 OF 71

Prior to enrollment, the investigative site should provide contact information and detailed instructions to subjects on how to withdraw from the study. When a subject is withdrawn, all data obtained prior to the time of withdrawal may be submitted to the Study Sponsor and be included in the study database, unless otherwise requested by the subject in writing.

In the event a subject is lost to follow-up or cannot be contacted for post-treatment assessments, at least three attempts (two phone calls and a certified letter) will be made to locate the study subject, and these efforts will be documented. If the subject cannot be located, the subject's lost to follow-up status will be documented in the EDC and they will be exited from the clinical study.

Should the subject expire, an adverse event form and a study exit/withdrawal form must be completed. Physician assessment is required to determine if the cause of death was possibly, probably, or definitely related to the IVL System. If available, copies of the death certificate and/or an autopsy report should be included in the research records. The Investigator may need to provide written notification to the IRB/EC upon the death of the study subject, dependent on the IRB/EC policies.

	No.: CP 65007	REV. C
	TITLE: Disrupt PAD BTK II Study	
	CLASS: CLINICAL PROTOCOL	PAGE 38 OF 71

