## 6.8 Clinical Study Duration

Enrollment is anticipated to last approximately 24 months. Study subjects will be followed through hospital discharge, 30 days, and 6-, 12-, and 24-months post-procedure. Duplex ultrasound (DUS) assessments will be completed at 6 and 12 months. Total anticipated study duration is 48 months.

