## 7.9 Subject Withdrawal

A study subject has the right to discontinue participation at any time without penalty or loss of benefits to which the subject is otherwise entitled. A subject that has withdrawn from the study will be treated according to standard of medical care and will not be replaced.

Potential reasons for withdrawal from the study are, but not limited to:

- Subject lost to follow-up
  - Pregnancy
  - Subject meets exclusion criteria not previously recognized or newly developed
- Safety concerns regarding the device

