### 9.1 General Statistical Methods

Descriptive statistics will be provided in this clinical study. Analyses will be conducted at pre-specified time points including 30 days, 6, 12 and 24 months.

Categorical variables will be summarized by the number of observations available, frequency, and percentage. Unless otherwise noted, missing data will be excluded from the denominator. Comparisons will utilize a Chi-square test, or Fisher's exact test when 20% or more of expected cell frequencies are less than 5. Clinical outcomes analyzed at 30 days will be evaluated as categorical (binary) data. McNemar's chi-square may be used to assess within-subject changes in a bivariate response variable. Exact confidence intervals will be generated for estimates of proportions.

Continuous variables will be summarized by the mean, standard deviation, median, minimum, and maximum. Within-subject changes will be analyzed parametrically using the Paired t-test if the differences are normally distributed, or non-parametrically using the Sign-Rank Test if the differences are not normally distributed. Asymptotic confidence intervals will be generated for estimates of means.

Exploratory analyses and clarifications to the protocol specified analysis plan will be documented in the SAP. Statistical analyses will be performed using SAS System® Version 9.4 or higher.

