### 9.3 Sample Size Determination

The sample size was calculated based on the precision of the exact 2-sided 95% confidence interval (CI) of the primary effectiveness endpoint, using the LIBERTY 360 study results as a reference. The LIBERTY 360 study of endovascular interventions for PAD is one of the largest, real-world, core laboratory–adjudicated studies to include patients with varying degrees of PAD severity. Procedural Success for the RC 4-5 cohort of this large contemporary data set was 75.8% [71.9, 79.3] [20].

The calculation of the Disrupt PAD BTK II sample size was based on a procedural success estimate of 75.8%. Combined with a desired precision of +/- 5.8% and an alpha of 0.05 (95% CI), a sample size of 225 was selected to provide a probability width (“power”) of 0.827. Assuming a lost-to-follow-up rate of 10%, up to 250 subjects will be enrolled.

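### The loss-to-follow-up rule in Section 7.9.1 lets a site exit an unreachable subject without retrying at later visits or checking its records

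*Combined protocol and SAP*

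**What the plan says.** Section 7.9.1 opens the rule with "In the event a subject is lost to follow-up or cannot be contacted for post-treatment assessments" and then requires that "at least three attempts (two phone calls and a certified letter) will be made to locate the study subject", with the efforts documented. If the subject still cannot be located, the "lost to follow-up status will be documented in the EDC and they will be exited from the clinical study". Section 7.9 lists "Subject lost to follow-up" among the reasons for withdrawal and does not replace withdrawn subjects. For a withdrawn subject, 7.9.1 provides that "all data obtained prior to the time of withdrawal may be submitted to the Study Sponsor"; it is silent on anything that comes to light afterwards.

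After discharge, Section 6.8 schedules follow-up at "30 days, and 6-, 12-, and 24-months post-procedure". Section 9.1 states that, unless otherwise noted, "missing data will be excluded from the denominator". Section 9.5 rules out imputation or adjustment in the primary analyses and, in time-to-event analyses, censors event-free subjects when last followed. Section 9.3 allows for attrition with "Assuming a lost-to-follow-up rate of 10" percent, which takes 225 subjects to 250.

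**The concern.** A failed contact at one visit does not mean that a subject is gone for good. Someone in another hospital around day 30 may be reachable at 6 months. That subject could then supply the later assessments and the dates of any death, amputation or reintervention in the gap. The exit rule does not require anyone to look.

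This matters because the study reports estimates with confidence intervals and has no control arm, so a distorted denominator feeds directly into the reported rate. Section 3.2 presents long-term follow-up as an advance on the earlier BTK study, and that is the part most exposed. Rutherford category 3 is capped at 20% of enrollment, so most subjects will be category 4 or 5. In them, being unreachable could plausibly be linked to poor outcome, although the documents offer no evidence that it is.

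**Working it through.** **1. The plan's own figure.** Inputs from Section 9.3: 225 subjects and 10% loss. 225 / (1 − 0.10) = 250, which matches the stated enrollment. Planned losses are 250 − 225 = 25. Section 9.3 does not tie the 10% to any timepoint.

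**2. What stands between a failed contact and exit.** Reading 7.9 and 7.9.1 together:
- Minimum number of missed visits: none stated.
- Waiting period, or deferral to the end of follow-up: none stated.
- Renewed contact at the next window: not required.
- Return to the study if the subject is found: no provision.
- Check of site records for vital status, amputation or revascularization: not required. Death certificates are mentioned only for a death already known.

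**3. Visits forgone.** There are four scheduled visits after discharge. Exit after a failed 30-day contact forgoes 3 more, after 6 months 2, and after 12 months 1.

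**4. Which endpoints are exposed.**
- Primary effectiveness is read by the core lab at the end of the procedure, so it is unaffected.
- The components of 30-day MALE/POD (death, above-ankle amputation, major reintervention) are dated events and could be established later.
- 30-day ABI/TBI, Rutherford category, questionnaire and wound status cannot be recovered once the window has passed. No duplex scan is scheduled at 30 days.
- All 6-, 12- and 24-month endpoints depend on visits or ascertainment that the exit may end.

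**5. Size, for a proportion.** Let *f* be the fraction lost by a timepoint, *p* the event rate in retained subjects and *q* the rate in lost subjects. The overall rate is (1 − *f*)*p* + *fq*, and the retained-only estimate is too low by *f*(*q* − *p*). Take *f* = 0.10 as an assumption.
- *q* = *p*: 0.10 × 0 = 0, no bias.
- *p* = 0.10, *q* = 2*p*: 0.90 × 0.10 + 0.10 × 0.20 = 11%.
- *p* = 0.10, *q* = 3*p*: 0.90 × 0.10 + 0.10 × 0.30 = 12%.
- *p* = 0.10, nothing assumed about *q* (0 to 1): 0.90 × 0.10 = 9% up to 9% + 10% = 19%.
- *p* = 0.20, nothing assumed about *q*: 0.90 × 0.20 = 18% up to 18% + 10% = 28%.

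**6. The share due to the rule.** Step 5 measures all missingness at a timepoint; the rule is responsible only for what would otherwise be recovered. If half were recovered (assumed), *f* = 0.05. Holding the observed rate at 10%, the range narrows to 0.95 × 0.10 = 9.5% up to 9.5% + 5% = 14.5%.

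**7. The 30-day safety endpoint.** Assume 7 events in 225 (3.1%) and a 10% to 20% rate in lost subjects. Holding 3.1% fixed:
- 5 lost by day 30 (*f* = 5/250 = 0.02): 0.02 × 0.069 to 0.02 × 0.169 = 0.1 to 0.3 points.
- 10 lost (*f* = 0.04): 0.04 × 0.069 to 0.04 × 0.169 = 0.3 to 0.7 points.
- All 25 lost by day 30 (*f* = 0.10): 0.7 to 1.7 points. This is an extreme, since the allowance carries no date and follow-up runs to 24 months.

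**The case against.** A reader might infer that one missed visit means permanent exit after exactly three attempts, that the outcomes are then lost, and that this falls mostly on subjects who did badly. The documents do not support that reading.
- The trigger refers to assessments in the plural. Three attempts is a minimum, with no timing, so they could span several windows. Exit follows only if the subject cannot be located, so a subject who misses a visit but can be found is not exited. Neither a single-visit threshold nor permanence is written down; both would be read into silence.
- Section 10.4 collects adverse events through 24 months and requires serious ones to be reported once site staff learn of them. Section 7.8.6 sends angiographic images from target-limb procedures during follow-up to the core lab. Section 11.4 asks for reasonable efforts to learn why a subject withdrew early. None of these is said to end at exit.
- Censored subjects contribute to time-to-event analyses until last follow-up, so there the issue is narrower: whether censoring is informative.
- Nothing in the documents shows that lost subjects fare worse.

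All of this stands as a limit on the claim, but it does not remove the gap. The minimum permits further attempts without requiring them, and sites may apply the silence differently. The event and image provisions depend on the site happening to learn of something, and they are not reconciled with a data rule that mentions only what was obtained before withdrawal. They supply no duplex, wound, ABI/TBI or questionnaire data and do not confirm that a subject is event-free.

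**Conclusion.** The concern holds in a limited form. As written, Section 7.9.1 allows exit after a failed 30-day contact, with up to three later visits forgone, and requires neither later contact nor a records check. The analysis then relies on retained subjects or on censoring.

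The weight falls on the 6-, 12- and 24-month secondary endpoints. The 30-day safety endpoint is affected only through dated events that could have been ascertained later. Primary effectiveness is not affected.

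No size or direction of bias can be taken from the documents. With equal risk in lost subjects there is no bias, only a loss of precision. With 10% lost by a timepoint, an observed 10% event rate is compatible with 9% to 19% overall. That range covers all missing data, of which the exit rule accounts for only the recoverable part. A 30-day shortfall as large as 1.7 points should not be claimed: it puts every planned loss at day 30, attributes all of it to this rule, and rests on an assumed event rate. The change is worth making because it is cheap, not because a large bias has been shown.

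**What to change.** Amend Section 7.9.1 as follows:
- Record a subject who cannot be reached as having missed that visit, and keep the subject in the study.
- Attempt contact again at each later scheduled window.
- Declare loss to follow-up only after the 24-month window closes, and after the site has checked its records for vital status, target-limb amputation and revascularization, as consent and local rules allow.
- State that event reporting under Section 10.4 and image submission under Section 7.8.6 continue for such subjects.

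The cost is a protocol wording change, plus a few more calls and a chart check per unreachable subject by existing site staff. No visit or procedure is added. The downside is that some subjects stay open in the database longer.

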## 8.0 BENEFITS AND RISKS

---

### 8.1 Anticipated Clinical Benefits

There may be no additional benefit from participation since subjects can receive IVL treatment per standard of care. The clinical study will provide safety and effectiveness data associated with Peripheral IVL System treatment of calcified BTK arteries. These clinical results may inform physicians in determining the optimal treatment strategy for this patient population.

### 8.2 Anticipated Adverse Device Effects

For detailed information on the risks of the devices used in the study procedure, including a complete list of warnings, precautions, and potential adverse events, please refer to the Instructions for Use (IFU) for the Peripheral IVL System. There are specific IFUs and labelling provided for the US and for OUS.

It is important to ensure that the IFU referred to represents the generation of the device used in the study procedure. Unanticipated risks can occur.

Possible adverse effects are consistent with standard angioplasty. Risks identified as unique to the device and its use are outlined in the IFUs for the M, M5+, and S IVL catheters. They include:

- Allergic/immunologic reaction to the catheter material(s) or coating [Incidence is Uncommon or Infrequent ( $\geq 0.1\%$  to  $<1\%$ )]
- Device malfunction or failure [Incidence is Rare ( $\geq 0.01\%$  to  $<0.1\%$ )]
- Excess heat at target site due to malfunction of IVL Generator\*

\*Note: Because of testing and clinical evidence, this risk is being removed from later revisions of the IFU.

### 8.3 Risks Associated with Participation in the Clinical Investigation

All assessments (with the exception of questionnaires) are considered to be standard of care, but may be conducted more frequently to comply with the follow-up visit schedule. Non-invasive testing includes physical exams, ABI/TBI, Rutherford Category assessments, wound healing assessments, and duplex ultrasounds. All of this testing poses minimal risk to the subject. The VascuQol questionnaire may not be standard of care at all centers; however, the assessment is non-invasive, introduces no additional risk, and is not considered to be an additional burden to the subject. For procedure-related risks, please refer to the current IFUs.

A risk management plan was established to outline the study-specific approach that will be implemented to focus on specific risks and area(s) of greatest need, which are considered to have the most potential to impact subject safety and data quality.

### 8.4 Possible Interactions with Concomitant Medical Treatments

There are no known possible interactions within this study.

	No.: CP 65007	REV. C
	TITLE: Disrupt PAD BTK II Study	
	CLASS: CLINICAL PROTOCOL	PAGE 39 OF 71

## 8.5 Steps that will be taken to Control or Mitigate the Risks

Only those subjects meeting each inclusion and no exclusion criteria will be enrolled into this clinical study. Investigators will be qualified by education, training, and experience to assume responsibility for the proper conduct of the clinical investigation. Risks of observed or theoretical adverse events will be mitigated through the Instructions for Use, physician training, subject selection in the study protocol, and close monitoring of protocol adherence.

All efforts will be made to minimize risks specifically by:

- Site selection
- Ensuring compliance to the protocol and IFU
- Data Review
- Study monitoring
- Statistical Evaluation
- Vendor Management
- Safety processes – protocol adverse event reporting requirements, CEC oversight, and safety reporting to regulatory authorities including Vigilance reporting
- Review of all device malfunctions and complaints by Shockwave Medical Quality. Risk acceptability thresholds and trend identification methods have been established, and actions will be taken if those are met.

## 8.6 Rationale for Benefit-Risk Ratio

The Shockwave Peripheral IVL System is market approved for the United States (US) and the European Union (EU) markets and will be used as per standard of care (SOC) at the investigational sites. The safety profile of the Shockwave Peripheral IVL System is well understood and the system is already used as part of standard of care at many sites. Previous clinical investigations have shown that the Shockwave Peripheral IVL System is safe and effective.

Risks and benefits of the Shockwave Peripheral IVL System are evaluated throughout the lifetime of the device as part of the risk management process in accordance with ISO 14971 which includes risk analysis, risk-to-benefit assessment, and risk control. Risk management activities, documentation, and records are held and/or referenced in the Risk Management File. The benefit-risk analysis provides objective evidence that all risks have been reduced as low as possible and no individual risks are unacceptable. Results indicated that the benefits of using the Shockwave Peripheral IVL System outweigh any residual risks.

	No.: CP 65007	REV. C
	TITLE: Disrupt PAD BTK II Study	
	CLASS: CLINICAL PROTOCOL	PAGE 40 OF 71

## 9.0 DATA ANALYSIS PLAN

---

### 9.1 General Statistical Methods

Descriptive statistics will be provided in this clinical study. Analyses will be conducted at pre-specified time points including 30 days, 6, 12 and 24 months.

Categorical variables will be summarized by the number of observations available, frequency, and percentage. Unless otherwise noted, missing data will be excluded from the denominator. Comparisons will utilize a Chi-square test, or Fisher's exact test when 20% or more of expected cell frequencies are less than 5. Clinical outcomes analyzed at 30 days will be evaluated as categorical (binary) data. McNemar's chi-square may be used to assess within-subject changes in a bivariate response variable. Exact confidence intervals will be generated for estimates of proportions.

Continuous variables will be summarized by the mean, standard deviation, median, minimum, and maximum. Within-subject changes will be analyzed parametrically using the Paired t-test if the differences are normally distributed, or non-parametrically using the Sign-Rank Test if the differences are not normally distributed. Asymptotic confidence intervals will be generated for estimates of means.

Exploratory analyses and clarifications to the protocol specified analysis plan will be documented in the SAP. Statistical analyses will be performed using SAS System® Version 9.4 or higher.

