Secondary Endpoints:	
 
Serious angiographic complications (flow-limiting dissection, perforation, distal embolization, or acute vessel closure) as assessed by the angiographic core lab
 
Lesion Success defined as final residual stenosis ≤50% in the target lesion without serious angiographic complications as assessed by the angiographic core lab
 
Primary Patency at 6 and 12 months (assessed for subject and lesion) defined as the absence of both total occlusion (100% diameter stenosis as assessed by DUS core lab) in all of the target lesions in a flow pathway, as well as any CEC adjudicated Clinically-Driven Target Lesion Revascularization (CD-TLR)
 
Clinically-Driven Target Lesion Revascularization (CD-TLR), CEC adjudicated, at 30 days, 6, 12, & 24 months
 
Major Adverse Events (MAE), CEC adjudicated at 30 days defined as a composite of: 
 
Need for emergency surgical revascularization of target limb
 
Unplanned target limb major amputation (above the ankle)
 
Symptomatic thrombus or distal emboli that require surgical, mechanical, or pharmacologic means to improve flow, and extend hospitalization
 
Perforations that require an intervention, including bail-out stenting
 
 
 
Quality of Life (QoL) assessed by VascuQoL questionnaire at 30 days, 6, 12, & 24 months, reported as change from baseline
 
Ankle-brachial index (ABI) or toe-brachial index (TBI) at 30 days, 6, 12, & 24 months, reported as change from baseline
 
Major Target Limb Amputation, CEC adjudicated, at 30 days, 6, 12, & 24 months
 
Rutherford Category at 30 days, 6, 12, & 24 months, reported as change from baseline
 

	No.: CP 65007	REV. C
	TITLE: Disrupt PAD BTK II Study	
	CLASS: CLINICAL PROTOCOL	

	
 
• Number of existing, new, and recurrent wounds at 30 days, 6, 12, & 24 months
 
• Number of healed wounds at 30 days, 6, 12, & 24 months
 
• Number of non-healed wounds by category (improving, stagnant, worsening) at 30 days, 6, 12, & 24 months
 

IVUS Sub-study	
 
• Up to 50 subjects; IVUS required at baseline, immediately post-IVL, and end of procedure
 

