### 5.2 Secondary Endpoints

- Serious angiographic complications (flow-limiting dissection, perforation, distal embolization, or acute vessel closure) as assessed by the angiographic core lab
- Lesion Success defined as final residual stenosis  $\leq 50\%$  in the target lesion without serious angiographic complications as assessed by the angiographic core lab
- Primary Patency at 6 and 12 months as assessed by both subject and lesion level defined as the absence of both total occlusion (100% diameter stenosis as assessed by DUS core lab) in all of the target lesions in a flow pathway, as well as any CEC adjudicated Clinically-Driven Target Lesion Revascularization (CD-TLR)
- Clinically-Driven Target Lesion Revascularization (CD-TLR), CEC adjudicated, at 30 days, 6, 12, & 24 months
- Major Adverse Events (MAE), CEC adjudicated, at 30 days defined as a composite of:
  - Need for emergency surgical revascularization of target limb
  - Unplanned target limb major amputation (above the ankle)
  - Symptomatic thrombus or distal emboli that require surgical, mechanical, or pharmacologic means to improve flow, and extend hospitalization

	No.: CP 65007	REV. C
	TITLE: Disrupt PAD BTK II Study	
	CLASS: CLINICAL PROTOCOL	PAGE 20 OF 71

- Perforations that require an intervention, including bail-out stenting
- Quality of Life (QoL) assessed by VascuQoL questionnaire at 30 days, 6, 12, & 24 months, reported as change from baseline
- Major Target Limb Amputation, CEC adjudicated, at 30 days, 6, 12, & 24 months
- Ankle-brachial index (ABI) or toe-brachial index (TBI) at 30 days, 6, 12, & 24 months, reported as change from baseline
- Rutherford Category at 30 days, 6, 12, & 24 months, reported as change from baseline
- Number of existing, new, and recurrent wounds at 30 days, 6, 12, & 24 months
- Number of healed wounds at 30 days, 6, 12, & 24 months
- Number of non-healed wounds by category (improving, stagnant, worsening) at 30 days, 6, 12, & 24 months

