## 6.7 Number of Subjects

Up to 250 subjects with moderate to severe calcified peripheral artery disease below the knee presenting with Rutherford Category (RC) 3 to 5 will be enrolled. The RC 3 will be capped at 20% of total enrollment. If a subject has a target lesion in each limb and one of the limbs is RC 3, this subject will count toward the Rutherford Category 3 cap. Up to two (2) target lesions allowed for each subject. Each site will be allowed to enroll up to 15% (37 subjects) of total study enrollment.

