##### Angiographic Inclusion Criteria

6. Up to 2 below-the-knee target lesion(s) in native vessels in one or both limbs.
7. Target lesion from the distal segment (P3) of the popliteal artery to the ankle joint.

	No.: CP 65007	REV. C
	TITLE: Disrupt PAD BTK II Study	
	CLASS: CLINICAL PROTOCOL	PAGE 24 OF 71

8. Target lesion reference vessel diameter (RVD) between 2.0mm and 4.0mm by investigator visual estimate.
9. Target lesion with  $\geq 70\%$  stenosis by investigator visual estimate.
10. Target lesion length is  $\leq 200\text{mm}$  by investigator visual estimate. Target lesion can be all or part of the 200mm treated zone.
11. Distal reconstitution of at least one pedal vessel ( $<50\%$  stenosis) (desert foot excluded) in the target limb.
12. Evidence of at least moderate calcification at the target lesion site by angiography/IVUS OR non-dilatable lesion indicating presence of calcium. Must meet one of the following:
  - a. Angiography requires fluoroscopic evidence of calcification on parallel sides of the vessel and extending  $>50\%$  the length of the lesion.:
  - b. IVUS requires presence of  $\geq 270$  degrees of calcium over the course of at least 10mm.
  - c. Non-dilatable lesion requires attempted treatment with PTA during the index procedure with residual stenosis  $>50\%$  and no serious angiographic complications.

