#### **7.7.4 Tandem Lesion(s)**

Tandem lesions (lesions  $< 3$  cm apart) are allowed if the total treated area covers the entire diseased segment. Total treated area is defined as the area treated by any PTA device (pre-dilatation, IVL, post-dilatation, or DCB). Each tandem lesion/diseased segment is considered one target lesion. As tandem lesions are considered one single target lesion, angiographic eligibility must be met as a single lesion.

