### 9.2 Primary Endpoints

Exact 95% confidence intervals will be generated for primary endpoints and estimates of proportions.

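### The exact-interval rule covers lesion-level proportions but ignores that one subject can contribute two lesions

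*Combined protocol and SAP*

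**What the plan says.** Section 9.1 (General Statistical Methods) gives the rule for proportions: "Exact confidence intervals will be generated for estimates of proportions". Section 9.2 repeats it with the confidence level: "Exact 95% confidence intervals will be generated for primary endpoints and estimates of proportions". Neither section distinguishes endpoints counted per subject from endpoints counted per lesion.

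The design allows more than one lesion per subject. Section 6.7 says "Up to two (2) target lesions allowed for each subject", and the angiographic inclusion criteria in Section 7.2.1 read "Up to 2 below-the-knee target lesion(s) in native vessels in one or both limbs". Section 7.7.4 limits the number of pairs by merging lesions less than 3 cm apart: "Each tandem lesion/diseased segment is considered one target lesion".

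Two secondary endpoints are lesion-level:

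- Lesion Success, in the Study Summary and Section 5.2: "Lesion Success defined as final residual stenosis ≤50% in the target lesion", also requiring freedom from serious angiographic complications.
- Primary patency, in Section 5.2: "Primary Patency at 6 and 12 months as assessed by both subject and lesion level". The text does not say whether this is a proportion or a time-to-event estimate.

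Section 9 names no method for correlated lesions. The McNemar and paired tests in Section 9.1 concern change within a subject over time. Section 9.1 also says: "Exploratory analyses and clarifications to the protocol specified analysis plan will be documented in the SAP". No separate SAP text was available, so this point concerns the rule as it stands in the protocol.

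**The concern.** An exact binomial interval is valid for independent observations. Two lesions in one subject share the patient, the operator and the procedure, so positive correlation between their outcomes is plausible, although the documents do not quantify it. With positive correlation, a set of lesions carries less information than its count suggests, and an interval built on the count overstates precision.

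The study has no formal hypothesis test, so the interval is the only statement of precision a reader gets. What is at stake is the honesty of the intervals around Lesion Success and, if it is reported as a proportion, lesion-level patency. The share of two-lesion subjects will be known only after enrolment, so it is better to settle the method beforehand.

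**Working it through.** **The plan's own figures.** The plan gives no precision figure for any lesion-level endpoint. Its sample size (Section 9.3: 225 evaluable, 75.8% success, ±5.8 points, probability 0.827) concerns the subject-level primary endpoint. 225 / 0.9 = 250 reproduces. The 0.827 is obtained with a normal-approximation interval (0.8273) and not with an exact one (0.508). That is a separate matter and does not enter below.

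**Inputs from the documents**

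- Subjects: 225 and 250 (Section 9.3).
- Maximum lesions per subject: 2 (Section 6.7).
- Share with two lesions: not given for this study. The only guide is an earlier cohort with 114 arteries in 101 patients (Section 3.1.2), so (114 − 101)/101 = 13/101, about 13%, if no patient had more than two.
- Success rate: 75.8% is a subject-level planning rate (Section 9.3). The only lesion-level rate is 99%, from that same earlier cohort.

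**Assumptions.** Shares of 13%, 20%, 30% and 50%; ICC of 0.3, 0.5 and 1; success rates of 75.8%, 90%, 95% and 99%.

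**Step 1: design effect.** For subjects with m = 1 or 2 lesions,

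DEFF = 1 + ICC × (Σm²/Σm − 1).

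With 225 subjects and 29 pairs (13%) there are 196 + 58 = 254 lesions, and Σm² = 196 + 4 × 29 = 312. At ICC 0.5, DEFF = 1 + 0.5 × (312/254 − 1) = 1.114. The interval should be wider by the factor √1.114 = 1.056.

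| Share with two lesions | Lesions | DEFF (ICC 0.5) | Widening | Exact half-width at 75.8%: unadjusted → on lesions/DEFF |
|---|---|---|---|---|
| 13% | 254 | 1.114 | 6% | 5.44 → 5.75 points |
| 30% | 293 | 1.232 | 11% | 5.06 → 5.63 points |
| 50% | 337 | 1.332 | 15% | 4.71 → 5.45 points |

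With 250 subjects the half-widths are 5.16 → 5.45, 4.79 → 5.33 and 4.46 → 5.16 points.

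**Step 2: true coverage of the unadjusted interval.** The distribution of the number of successful lesions was enumerated exactly. Single-lesion subjects are Bernoulli(p). In a pair, P(both succeed) = p² + ICC·p(1 − p), P(both fail) = (1 − p)² + ICC·p(1 − p), and P(one of each) = 2p(1 − p)(1 − ICC). Coverage is the probability that the Clopper-Pearson interval on all lesions contains p. Ranges are over 225 and 250 subjects and p = 75.8%, 90% and 95%.

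| Share with two lesions | ICC 0.3 | ICC 0.5 |
|---|---|---|
| 13% | 94.6-96.7% | 94.1-96.4% |
| 20% | 94.3-95.8% | 93.5-95.2% |
| 30% | 94.0-94.6% | 93.0-93.6% |
| 50% | 93.0-95.0% | 91.4-93.7% |

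**Step 3: p = 99%.** The exact interval is conservative near 100%, and this absorbs most of the correlation. For 225 / 250 subjects:

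| Share with two lesions | ICC 0.5 | ICC 1 |
|---|---|---|
| 13% | 98.0 / 96.8% | 97.4 / 96.2% |
| 30% | 98.1 / 97.0% | 97.2 / 95.9% |
| 50% | 96.0 / 92.7% | 94.4 / 87.5% |

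There is no shortfall at 13% or 30%. One can appear at 50%.

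**The case against.** The strongest reply is that at the documents' own figures nothing is lost. With 13% pairs and a 99% lesion-level rate, the unadjusted interval over-covers even at ICC 1, and with 13% pairs and ICC 0.5 it is close to nominal at the lower rates too. The tandem rule reduces pairs further. Nothing decisive rests on these intervals: the study is descriptive, Procedure Success is already defined over all of a subject's treated target lesions, and patency is also reported per subject, so each lesion-level result has a subject-level counterpart free of clustering. Section 9.1 leaves clarifications to the SAP, which may already deal with this. Patency may turn out to be a time-to-event estimate, which the exact-interval rule would not govern.

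Most of this stands, and it sets the weight of the point. It does not remove it. The 13% and the 99% come from an earlier cohort followed only to discharge; the documents give no 6- or 12-month lesion patency rate, so the reassurance at 99% does not carry over to patency. Only Lesion Success is a certain instance. If the SAP already states a clustered interval, confirming that closes the point.

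**Conclusion.** The point holds, at minor severity. As written, the rule applies an independent-observation interval to lesion counts in a design that permits two lesions per subject. The resulting intervals are somewhat too narrow if outcomes within a subject correlate positively and pairs are common. The pair share, the ICC and the lesion-level rates are all assumptions here. Under them the effect runs from negligible at about 13% pairs to a coverage loss of roughly one to four points at 50% pairs and ICC 0.5, for success rates of 75.8% to 95%. Both primary endpoints and their intervals, the sample size and every point estimate are unaffected.

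**What to change.** Keep exact intervals for subject-level proportions. For lesion-level proportions, state in the SAP:

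- A subject-clustered interval: Clopper-Pearson on an effective sample size of lesions / DEFF, with the ICC estimated from the two-lesion subjects and truncated to 0-1.
- A rule for sparse data: with too few failures to estimate the ICC (for example, fewer than 5 failed lesions), set it to 1. This also works with zero failures, where a logit-scale GEE does not.
- Whether lesion-level patency is a proportion or a time-to-event estimate and, in the latter case, a subject-clustered variance.
- That the number of two-lesion subjects will be reported.

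Evaluated with the ICC estimated rather than known, over shares of 13%, 30% and 50%, this interval covers 95.2-97.3% for success rates of 75.8% to 95% (ICC 0 to 1) and 97.9-98.8% at 99% (ICC 0.3 to 1).

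The cost is SAP wording, with no new data. Half-widths grow by about 0.3 to 0.7 points at 75.8% and ICC 0.5. At 99% and ICC 0.5 the sparse-data rule applies in 67-88% of data sets, and the mean half-width with 225 subjects rises by about 0.2 to 0.4 points (1.43 to 1.62, 1.31 to 1.64 and 1.21 to 1.60 at the three shares), which is mildly conservative there. Another subject-clustered method would also serve, provided it is named in advance and copes with few or no failures.
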